### 10.3 Randomization and Stratification

The three dose cohorts will enroll sequentially. Within each cohort, 15 eligible participants will be randomized 4:1 to receive cemiplimab (n=12) or placebo (n=3). Randomization will use the permuted block method without institutional balancing or stratification. After enrollment of each dose cohort is complete, study enrollment will be suspended until a decision is made on opening the next (higher dose) cohort to enrollment, based on the dose escalation criterion and SMC review.

### 10.4 Sample Size and Accrual

The total sample size of this study is 45 evaluable participants. Within each dose cohort, there will be 12 active-treated participants and 3 placebo participants. Ultimately, there will be a total of nine placebo recipients for comparison of immunologic and virologic outcomes. Participants who do not receive study treatment will be replaced. In addition, any participant who does not receive  $\geq 90\%$  of both study treatment infusions, or discontinues the study prior to week 12 without having met the primary safety endpoint ([section 10.2.1.1](#)), will be replaced.

#### 10.4.1 Safety

The criteria to be used to guide the SMC when determining dose resumption or dose escalation for each cohort are defined as not having observed:

- A. Three or more active-treated participants have experienced a Grade  $\geq 3$  AE that is related to study treatment (as judged by the core team, blinded to treatment arm and by the SMC who will receive unblinded data);
- B. Two or more active-treated participants have experienced an irAE (not including an infusion reaction AE) that is related to study treatment (as judged by the core team, blinded to treatment arm, and by the SMC who will receive unblinded data) as defined by:
  - i Grade  $\geq 1$  pneumonitis, adrenal insufficiency, myocarditis, diabetes, or uveitis;
  - ii Grade  $\geq 2$  colitis, myositis, rash, hyperthyroidism or hypothyroidism, or elevated AST or ALT.
- C. One or more active-treated participants have experienced a Grade  $\geq 4$  clinical AE (excluding asymptomatic laboratory abnormalities) that is related to study treatment (as judged by the core team, blinded to treatment and by the SMC who will receive unblinded data).

NOTE A: Asymptomatic Grade 4 laboratory abnormalities are addressed within A.

NOTE B: The following probability calculations assume a deterministic dose-escalation rule and do not reflect the essential element of SMC review and clinical consideration by the SMC of the data presented with respect to dose-escalation decisions.

[Table 10.4.1-1](#) below shows the probabilities of dose escalation under various assumed true rates for the three types of AEs as described above, considering 12 participants receiving active treatment. In the table, the column “True participant-specific probability of AE event type A” is the probability of a Grade  $\geq 3$  AE conditional on not having an event of type C (Grade 4 or higher clinical AE). Similarly, the column “True participant-specific probability of AE event type B” is the probability of observing an irAE conditional on not having an event of type C. To calculate these probabilities of dose escalation, event types A and B were subdivided into three mutually exclusive groups: X=Grade  $\leq 2$  events in B, Y=Grade  $\geq 3$  events in B, and Z=Grade  $\geq 3$  events in A not part of B. Participant-specific probabilities of X, Y, and Z were assumed (conditional on not having an event of type C) and the events X, Y, and Z were assumed independent (conditional on not having an event of type C). Probabilities of A and B (conditional on not having an event of type C) as displayed in the table were each then calculated (i.e.,  $\text{Pr}(A|C=0) = \text{Pr}(Y|C=0) + \text{Pr}(Z|C=0) - \text{Pr}(Y|C=0)*\text{Pr}(Z|C=0)$ ). The probability of dose escalation was computed by numerical simulation with 100,000 replicates based on  $\text{Pr}(C)$ ,  $\text{Pr}(X|C=0)$ ,  $\text{Pr}(Y|C=0)$ , and  $\text{Pr}(Z|C=0)$  for each listed scenario in the table.

The proposed sample size provides a reasonably high probability of dose escalation when the true event rates are, in fact, acceptable. For example, if the probability of a participant in the active treatment arm of a given dose cohort experiencing an AE of type A as described above is 0.03 (3%), the probability of experiencing an AE listed in B above is 0.02 (2%) and the corresponding probability of experiencing a Grade 4 or higher AE as described in C above is 0.01 (1%), then the probability that the study will dose escalate to the next higher dose is 0.86 (86%). Given that this is an acceptable safety profile, this means that the probability of incorrectly concluding the current dose is unsafe is 0.14 (14%). On the other hand, the proposed sample size provides a low probability of dose escalation when the true event rates are unacceptable. For example, if the probability of a participant in the active treatment arm of a given dose cohort experiencing an AE of type A as described above is 0.2 (20%), the probability of experiencing an AE listed in B above is 0.2 (20%) and the corresponding probability of experiencing a Grade 4 or higher AE as described in C above is 0.1 (10%), then the probability that the study will dose escalate to the next higher dose is 0.06 (6%); the corresponding probability of not dose escalating and correctly concluding the dose unsafe is 0.94 (1-0.06).

Table 10.4.1-1: Probabilities of Meeting the Dose Escalation Criterion under Various Assumed True Rates

True Participant-specific Probability of AE Type A (Grade $\geq 3$ AE related to study drug)	True Participant-specific Probability of AE Type B (irAE related to study drug)	True Participant-specific Probability of AE Type C (Grade 4 or higher clinical AE related to study drug)	Probability of Dose Escalation Criterion
0.008	0.009	0.005	0.94
0.03	0.02	0.01	0.86
0.03	0.02	0.02	0.76
0.04	0.04	0.03	0.64
0.06	0.06	0.05	0.44
0.14	0.10	0.07	0.22
0.18	0.18	0.08	0.11
0.20	0.20	0.10	0.06
0.25	0.25	0.15	0.015

Considering 12 treated participants in a cohort, Table 10.4.1-2 displays the probability of observing at least one participant with an event, and the probability of observing at least two participants with an event, for various underlying event probabilities. For example, consider an irAE as the event. Then 12 treated participants provides >70% likelihood of observing such an event if the participant-specific probability is at least 0.10 (10%).

Table 10.4.1-2: Probability of Observing at Least One Participant with an Event, and the Probability of Observing at Least Two Participants with an Event, for Various Underlying Event Probabilities

Participant-specific Probability of Event	Probability of Observing $\geq 1$ Participant with Event, N=12 Treated	Probability of Observing $\geq 2$ Participants with an Event, N=12 Treated
.1	0.72	0.34
.2	0.93	0.73
.3	0.99	0.91

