#### Assessment Prior to Week 6 Cemiplimab/Placebo Administration

Prior to administering the second infusion at week 6 in all dose cohorts, the safety-related items in [sections 4.1](#) and [4.2](#) should be re-assessed by a site investigator or designee based on the week 4 evaluations (or the visit prior to the week 6 infusion, as appropriate). If the following are not confirmed, then the second infusion should not be given:

- Negative results for TPO antibody, GAD65/GAD antibody, and islet cell antibody.
- Negative or within normal range results for metabolic studies (fasting glucose, AM cortisol, TSH, and free T4).

These must be done at a laboratory that possesses a CLIA certification or equivalent.

Also, if any irAEs were identified following the first infusion or suspected irAEs are under investigation for relatedness, the second infusion must not be given.

NOTE A: If enrollment safety pause criteria are met (see [section 10.4.1](#)), participants already enrolled on study should not receive the second infusion pending SMC review, but should be followed for safety per NOTE B above. The study leadership will notify sites if and when a safety pause is needed and will also notify sites when the pause is lifted.

NOTE B: If enrollment is re-opened following SMC review, the above safety labs designated for week 4 should be repeated if collected >4 weeks prior to the rescheduled second infusion.

This information should be captured on the appropriate eCRF.

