### Adverse Events of Special Interest (AESI)

An AESI (serious or non-serious) is one of scientific and medical concern specific to the sponsor's product or program, for which ongoing monitoring and rapid communication by the investigator to the sponsor can be appropriate. Such an event might warrant further investigation in order to characterize and understand it. Depending on the nature of the event, rapid communication by the trial sponsor to other parties (e.g., regulators) might also be warranted.

AESIs include all cases of irAEs, felt to be related to study treatment, including:

- Grade 2 or greater infusion-related reactions
- Grade 2 or greater allergic/hypersensitivity reactions
- All irAEs regardless of grade, including but not limited to: dermatitis, pneumonitis, myocarditis, colitis, adrenal insufficiency/crisis, hypo- or hyperthyroidism, thyroiditis, diabetes, hypophysitis, hepatitis, systemic lupus erythematosus, nephritis, myasthenia gravis, and/or drug-induced liver injury (DILI)

For all AESIs, the core team should be contacted immediately via email at [[contact]](mailto:[contact]) (See [section 7.3.2](#)).

NOTE: Participants with an ongoing AESI at week 48, should be followed until the AE has resolved or stabilized in the opinion of the core team (see [section 6.2.4](#)).

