8.3.7 Suspected Immune-related Renal Dysfunction

For participants with worsening renal function, the following should be obtained: repeat BUN, serum creatinine, and serum electrolytes within 48 hours of the first abnormal value. For any suspected immune-related renal toxicity, WITHHOLD further doses of cemiplimab/placebo until diagnostic evaluation has been completed and etiology of the signs and symptoms has been determined.

NOTE: The DAIDS AE Grading Table, corrected Version 2.1, July 2017, for grading creatinine should be used, and can be found on the DAIDS RSC website at <https://rsc.niaid.nih.gov/clinical-research-sites/daids-adverse-event-grading-tables>.

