### 8.3.8 Suspected Immune-related Neurologic Dysfunction

#### 8.3.8.1 Grades 1-4 Altered mental status, neuromuscular weakness, or seizures

- WITHHOLD further doses of cemiplimab/placebo until clinical and laboratory evaluation are completed and diagnosis and etiology of the symptoms or laboratory abnormalities are defined
- Immediately contact the core team via email at [[contact]](mailto:[contact])
- Perform appropriate diagnostics which may include but are not limited to imaging with MRI with contrast of affected region and CSF sampling
- Hospitalization as per standard of care
- Consult neurologist immediately
- Initiate systemic corticosteroids in consultation with a neurologist
- High-dose corticosteroids should be tapered, if used, in consultation with a neurologist.

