## 10.5 Data and Safety Monitoring

If at any time within a given dose cohort:

- a) Three or more participants experience a Grade  $\geq 3$  AE related to study treatment ([section 10.2.1.1](#)) (as judged by the core team, blinded to treatment arm); or
- b) Two or more participants experienced an irAE (not including an infusion reaction AE) ([see section 10.4.1B](#)) that is related to study treatment (as judged by the core team, blinded to treatment arm); or
- c) One or more participants experience a Grade 4 clinical AE or death and related to study treatment (as judged by the core team, blinded to treatment arm);

then enrollment into the study and treatment infusions will be temporarily suspended and the SMC, unblinded to treatment assignment, will be asked to review all safety data; review the relation to study treatment of the event(s) thought by the blinded core team to be a primary safety outcome; and recommend how the study should proceed with respect to resuming enrollment, continuing study treatment and dose escalation.

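### The automatic pause in 10.5(b) rests on closed event lists that leave out immune-related nephritis and neurologic events, and hypophysitis unless it is recorded under a listed term

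*Protocol*

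**What the plan says.** Section 10.5 opens its pause rule with "If at any time within a given dose cohort" and gives three triggers:

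- (a) three participants with a related Grade 3 or higher event;
- (b) "Two or more participants experienced an irAE (not including an infusion reaction AE"), with a cross-reference to 10.4.1B;
- (c) one related Grade 4 clinical event or death.

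Any trigger suspends enrolment and infusions until the unblinded study monitoring committee (SMC) has reviewed the data. Section 6.3.5 NOTE A spells out the effect on others: "participants already enrolled on study should not receive the second infusion pending SMC review".

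Section 10.4.1B defines the irAEs by two lists, neither with a catch-all. From Grade 1: "pneumonitis, adrenal insufficiency, myocarditis, diabetes, or uveitis". From Grade 2: "colitis, myositis, rash, hyperthyroidism or hypothyroidism, or elevated AST or ALT".

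Elsewhere the protocol's view of irAEs is wider. The list of events of special interest in 7.2 includes "diabetes, hypophysitis, hepatitis, systemic lupus erythematosus, nephritis, myasthenia gravis, and/or drug-induced liver injury (DILI"). Section 8.3.7 states: "For any suspected immune-related renal toxicity, WITHHOLD further doses of cemiplimab/placebo until diagnostic evaluation has been completed". Section 8.3.8.1 also withholds dosing, under the heading "Grades 1-4 Altered mental status, neuromuscular weakness, or seizures". The primary safety outcome (10.2.1.1) counts any related irAE of Grade 1 or above through an open-ended list.

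**The concern.** The protocol treats renal and neurologic irAEs and hypophysitis as irAEs, counts them in the primary outcome, and withholds the affected participant's dosing for suspected renal events and the main neurologic presentations. Yet they do not count toward the irAE pause. The resulting order is hard to defend clinically: two Grade 2 rashes stop everyone's infusions, while two Grade 3 cases of encephalitis or nephritis do not.

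At stake is the second infusion of other participants. The pause is the only automatic rule by which events in some participants stop dosing in others. The mandatory SMC review comes after the last participant in a cohort reaches week 12, by which time that cohort's second infusions have normally been given.

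**Working it through.** **1. The rule applied to pairs of related events in one cohort (no other related events)**

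| Two participants with | (a) needs 3 | (b) needs 2 | (c) needs 1 | Pause? |
|---|---|---|---|---|
| Grade 2 nephritis or neurologic irAE | 0 | 0 | 0 | No |
| Grade 3 nephritis or neurologic irAE | 2 | 0 | 0 | No |
| Grade 2 rash, or Grade 2 AST/ALT rise | 0 | 2 | 0 | Yes |

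**2. How many participants a pause could protect**

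Section 10.1 gives 3–4 months of accrual per cohort, which is 13.0–17.3 weeks at 52/12 weeks per month. Adding 6 weeks, second infusions run to week 19.0–23.3 after a cohort's first entry. With 15 participants entering evenly (an assumption), the number awaiting a second infusion during accrual is 15 × 6/13 = 6.9 down to 15 × 6/17.3 = 5.2. About 5.5 to 4.2 of them are on active drug.

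**3. How often two such events would arise**

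Table 2.2-1, all grades / Grades 3–5:

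| Term | Total (N=757) | Monotherapy (N=489) |
|---|---|---|
| Nephritis | 3/2 | 2/1 |
| Hypophysitis | 2/2 | 2/2 |
| Myasthenia gravis | 1/1 | 1/1 |
| Encephalitis | 2/2 | 1/1 |
| Meningitis | 2/2 | 1/1 |
| Chronic inflammatory demyelinating polyradiculoneuropathy | 1/0 | 1/0 |
| Peripheral neuropathy | 1/0 | 1/0 |
| Paraneoplastic encephalomyelitis | 1/1 | 1/1 |
| Sum | 13/10 | 10/7 |

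That leaves 13 − 10 = 3 and 10 − 7 = 3 at Grade 1–2. With 12 active participants, P(X ≥ 2) = 1 − (1−p)^12 − 12p(1−p)^11:

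- p = 3/757 = 0.0040: 1 − 0.9535 − 0.0455 = 0.0010
- p = 13/757 = 0.0172: 1 − 0.8123 − 0.1703 = 0.0174
- p = 3/489 = 0.0061: 1 − 0.9288 − 0.0688 = 0.0024
- p = 10/489 = 0.0204: 1 − 0.7804 − 0.1955 = 0.0241

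For hypophysitis, nephritis and myasthenia gravis alone (1 and 6 of 757), the results are 0.0001 and 0.0039. Each Grade 1–2 and all-grade pair brackets the Grade 1–3 figure, because the table pools Grades 3–5 and related Grade 4 clinical events already trip (c).

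**4. Effect of a longer list on the escalation criterion**

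First, the protocol's own figure. For the row Pr(A) = 0.03, Pr(B) = 0.02, Pr(C) = 0.01 the protocol states 0.86. Following the method in 10.4.1, and assuming half of B is Grade 3 or higher:

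- Given no C, Pr(Y) = 0.01, Pr(X) = 0.0101 and Pr(Z) = 0.0202.
- (1 − 0.01)^12 = 0.8864.
- P(at most two A and at most one B | no C) = 0.9736.
- Product: 0.863, which agrees with 0.86. A 25% or 75% share moves this by at most 0.001.

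Table 10.4.1-2 also reproduces: 0.718/0.341, 0.931/0.725 and 0.986/0.915.

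Next, raise the input Pr(B):

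- Adding 3/757 at Grade 1–2: 0.8864 × 0.9647 = 0.855. With 3/489: 0.850.
- Also moving the named Grade 3–5 events from Z into B, holding Pr(A) at 0.03: 0.8864 × 0.9291 = 0.824 for 10/757, and 0.814 for 7/489.
- In the unacceptable row (0.20/0.20/0.10) the 757-based figures go from 0.061 to 0.059 and 0.055.

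**The case against.** The strongest reply is that other oversight is dense. A participant with an irAE gets no second infusion (6.3.5, 9.1). Sites report any related irAE to the core team within 24 hours (8.0 NOTE C). The core team reviews participant-level data frequently, chairs may alert the SMC to notable Grade 3 events, and an interim review may be convened (7.4). A third related Grade 3 event of any kind trips (a), and one related Grade 4 clinical event trips (c). A separate Study Monitoring Plan, not at hand, may add more. All of this stands, but these steps act on the affected participant alone, are discretionary, or need further events. They narrow the gap without closing it.

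Second, hypophysitis is partly covered. Scheduled cortisol, TSH and free T4 testing means that a case with hormone deficiency may be recorded as adrenal insufficiency (listed from Grade 1) or hypothyroidism (listed from Grade 2). A reader might infer that hypophysitis never counts; the text does not support that. Myositis is listed too, so some cases of weakness may be caught. Nephritis and most central neurologic events have no such route.

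Third, adding a few names leaves another closed list. Systemic lupus erythematosus is in 7.2 but not in B. Table 2.2-1 also shows stomatitis (3), arthritis (2), and one each of pancreatitis, vasculitis, Sjögren's syndrome and immune thrombocytopenic purpura. This is fair, and is why a Grade 3 residual item is preferable.

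Fourth, benefit and cost rise together. If unlisted Grade 2 irAEs had a true rate of 2% or 5% (assumed values), counting them in B would lower 0.863 to 0.813 or 0.708. That is correct, though at such rates a pause for review is what one would want.

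**Conclusion.** The point holds as a gap in the automatic pause. Two related Grade 2 cases of an unlisted type meet no criterion, and two related Grade 3 cases reach only two of the three needed under (a). The expected frequency is low, about 0.1% to 2.4% per cohort. That range rests on oncology rates, 12 active participants, and counts of terms rather than distinct patients. The table holds only identified irAEs (steroid-treated or endocrine), so milder cases are missing, and rates in this population are unknown.

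Three stronger readings are not supported:

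- *Escalation could proceed despite such cases.* Section 3.0 makes escalation depend on the core team and SMC noting no safety concerns, and 7.4 requires unblinded SMC review. The 10.4.1 criteria only guide that decision.
- *Table 10.4.1-1 is wrong or must be re-run.* It is indexed by assumed Pr(A), Pr(B) and Pr(C). Lengthening the list changes which row applies, not any entry.
- *The predecessor anti-PD-L1 trial shows the pause would have failed.* Its single potential hypophysitis, at week 36 in one of six participants, would not trigger even an amended rule, which needs two participants in one cohort.

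This is a low-priority improvement, and no stated figure is in error.

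**What to change.** Amend 10.4.1B so that 10.5(b) inherits the change:

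- In B(i), add *Grade ≥1 hypophysitis*.
- In B(ii), add *Grade ≥2 immune-related nephritis, myasthenia gravis or other neurologic irAE*.
- Preferably, add a third item: *any other related irAE of Grade ≥3*.

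No entry in Table 10.4.1-1 changes. A sentence noting that the assumed Pr(B) now covers more event types would be enough. For the row now at 0.86, the criterion is met with probability about 0.85 at oncology rates, or 0.81–0.82 if the named Grade 3–5 events also count in B. It is lower if true rates exceed those, and somewhat lower again with the residual Grade 3 item, which was not computed.

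The cost is a short text amendment and an occasional extra precautionary pause with SMC review. Sample size and visits are unaffected.

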#### 10.4.2 Efficacy

For the secondary outcome measure of efficacy, statistical power is described for the paired t-test which will be used (two-sided, alpha=0.05), testing that CD8+ T cell responses ([10.2.2.1](#)) increase pre- to post-treatment among the active-treated study participants. The key assumption is that CD8+ T cell responses would be stable (mean change of zero) without intervention (i.e., with continued cART). Because estimates of the anticipated standard deviation (SD) of the change are not available, power is described in terms of SD units. With 11 evaluable treated participants in a dose group (allowing for one unevaluable, e.g., due to issues with the sample or assay), power is >80% to detect a treatment effect in a dose group if the mean change is at least 0.94 SD units; this

corresponds under assumed normality to a probability of 0.83 or larger that a participant would have an observed increase in CD8+ T cell responses after treatment (the null hypothesis is that the probability is 0.5, corresponding to zero mean change). Combining the three dose groups (n=33), power is >80% to detect a treatment effect of 0.504 SD units, corresponding to a probability of 0.69 or larger that a participant would have an observed increase in CD8+ T cell responses after treatment.

Adjustments for separate statistical testing in each of the dose cohorts have not been incorporated into power calculations for this study.

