### 1.3 Secondary Objectives

- 1.3.1 To evaluate the change in magnitude of HIV-1 gag-specific CD8+ T cells by intracellular staining for both CD107a and interferon gamma (IFN- $\gamma$ ) from a pre-treatment baseline level (average of 2 measurements) to time points after one or two doses of cemiplimab (average of responses from weeks 2, 4, 6, 8, 10, and 12).
- 1.3.2 To evaluate the change in magnitude of HIV-1 gag-specific CD8+ T cell responses using both CD107a and IFN- $\gamma$  expression from baseline to time points after the first dose of cemiplimab or placebo (average of responses from weeks 2, 4, and 6), and to time points after the second dose or placebo (average of responses from weeks 8, 10, and 12).
- 1.3.3 To evaluate the change in magnitude of HIV-1 gag-specific CD8+ T cells by intracellular staining for IFN- $\gamma$  or CD107a alone, from baseline (pre-treatment average) to time points after one or two sequential doses of cemiplimab or placebo (average of responses from weeks 2, 4, 6, 8, 10, and 12) and explore difference following each dose.
- 1.3.4 To evaluate changes in polyfunctional response of HIV-1-gag-specific CD8+ T cells by intracellular staining for IFN- $\gamma$ , CD107a, IL-2, and TNF $\alpha$  from baseline (pre-treatment average) to time points after one or two sequential doses of cemiplimab or placebo and explore difference following each dose.
- 1.3.5 To assess the durability of response to cemiplimab by evaluating the magnitude of HIV-1 gag-specific CD8+ T cell responses by intracellular staining of CD107a and IFN- $\gamma$  and polyfunctional response through week 48.

1.3.6 To assess immunogenicity to cemiplimab after multi-dose administration to cART-treated HIV-1-infected participants.

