#### *Summary*

The primary goal of this study is: 1) to test the safety of two doses of cemiplimab versus placebo in a dose rising fashion in participants on suppressive cART, and 2) to determine whether cemiplimab can improve HIV-1-specific cellular immune responses. In addition, we will evaluate the PK of cemiplimab in serum, and examine the time course of RO in whole blood. We plan to simultaneously measure and assess the impact of cemiplimab on: 1) HIV-1-specific T cell magnitude and function, 2) persistent viremia by SCA, and 3) additional measures of HIV-1 persistence in total CD4+ T cells from peripheral blood. Given that only a subset of cancer patients have responded to blockade of the PD-1/PD-L1 pathway in previous clinical trials, we will also explore whether ex vivo response to gag peptides in the presence of cemiplimab pre-treatment is associated with an in vivo response, to identify biomarker(s) predictive of a response to cemiplimab that could inform patient stratification in future studies [33].

If the goals of the study are achieved, the potential next steps would be a larger phase II multiple-dose study of cemiplimab, to further assess safety, HIV specific immune responses, and the impact on HIV reservoirs in blood and tissue, or studies in combination with latency reversing agents or HIV vaccines.

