## 10.0 STATISTICAL CONSIDERATIONS

### 10.1 General Design Issues

A5370 is a phase I/II, double-blinded (within each cohort), dose-escalating, placebo-controlled study of the safety and immunotherapeutic activity of two infusions of anti-PD-1 (cemiplimab) in HIV-1-infected participants on cART who have HIV-1 RNA below the limit of quantification and CD4+ T-cell counts  $\geq 350/\text{mm}^3$ . Each participant will be followed for 48 weeks, with frequent visits in the first 12 weeks. The decision to enroll into each successively higher dose cohort will be based on review of the safety data seen in participants who received cemiplimab or placebo doses in the previous dose cohorts (see [sections 7.4](#) and [10.4.1](#)). Accrual for each dose cohort is anticipated to take 3-4 months. Taking into account the time needed for data review regarding dose escalation between each cohort (data entry, core team review, SMC report generation, and SMC review) and assuming that all three cohorts complete enrollment, the total time to complete accrual is expected to be about 20 months. This may take longer if participant replacements are needed. Laboratory assays and study analyses may commence, and findings reported, after each cohort has completed accrual and follow-up through the week 12 visit.

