### 10.6.2 Secondary Analyses

For the HIV-1-specific CD8+ T cell efficacy outcome ([section 10.2.2.1](#)), post-treatment changes will be evaluated, comparing measurements at baseline (averaging the pre-treatment measures) to an average of post-treatment measurements through week 12, jointly analyzing the actively treated participants from all dose cohorts using the paired t-test. As supplemental analyses, the

same methods will separately analyze each dose cohort. The rationale to average over multiple post-treatment timepoints is that the timing and dynamics of treatment-induced immunologic (or virologic) effects is not known; the average of multiple time points aims to capture both early effects that may wane (for example, as seen in one of the immunologic responders to a single-dose of the anti-PD-L1 antibody [26]; or, for example, a response that only appears following the second infusion). Graphical approaches will display the means at each visit and mean changes from baseline to each follow-up visit (and separately to the average of weeks 2-6 and to weeks 8-12), by dose cohort and separately for the placebo participants. Longitudinal participant-specific plots will also be presented for each treatment dose and for the placebo participants.

Because the aim of this phase I/II study is to investigate the biologic effects of the treatment (anti-PD-1 antibody cemiplimab), efficacy analyses will be “as-treated” and also, to maximize the ability to identify treatment effects, efficacy analyses will be based only on participants who completed  $\geq 90\%$  of both study treatment infusions. In addition, if any participant interrupts cART for more than 7 consecutive days during the study, only measurements prior to cART interruption will be used in efficacy analyses.

Analyses of other immunologic and virologic measures will parallel the efficacy analyses as outlined above. For example, cell-associated HIV-1 RNA levels will be compared pre-treatment to post-treatment using paired t-tests separately by dose group (and for the combined treated participants) and for the placebo participants. Virologic measures such as cell-associated HIV-1 RNA will be log-transformed prior to analyses. Because low-level viremia as measured by SCA is anticipated to be below assay limit in a substantial fraction (~50%) of participants, binary (GEE) or censored-data [64] longitudinal analysis approaches are planned to assess treatment effects on SCA.

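### The CD8+ efficacy outcome is tested before versus after in active participants only and called a treatment effect; no cemiplimab-minus-placebo estimate is planned

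*Protocol*

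**What the plan says.** For the leading CD8+ outcome (10.2.2.1), Protocol 10.6.2 compares the averaged pre-treatment value with the average of post-treatment values through week 12, "jointly analyzing the actively treated participants from all dose cohorts using the paired t-test", with each dose cohort analysed separately as a supplement. Section 10.4.2 powers this test at two-sided 0.05, with 11 evaluable per dose group and 33 pooled. For the pooled analysis, "power is >80% to detect a treatment effect of 0.504 SD units". The condition attached is: "The key assumption is that CD8+ T cell responses would be stable (mean change of zero) without intervention".

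For this outcome 10.6.2 uses placebo only in displays. Means and mean changes are plotted "by dose cohort and separately for the placebo participants", and individual courses are plotted too. Other measures are to follow the same approach; the example given, cell-associated HIV-1 RNA, adds a separate paired t-test within placebo. No active-minus-placebo difference, interval or test is stated for either.

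Elsewhere the protocol gives placebo a larger part. Section 10.4 says "there will be a total of nine placebo recipients for comparison of immunologic and virologic outcomes". Section 10.1 describes a placebo-controlled study of safety and of immunotherapeutic activity. Objective 1.3.2 concerns CD8+ change "from baseline to time points after the first dose of cemiplimab or placebo". The Summary in section 2.2 sets the aim "to determine whether cemiplimab can improve HIV-1-specific cellular immune responses".

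**The concern.** Whether cemiplimab improves responses is a causal question, and a before-after change in treated people answers it only if nothing else would have moved the response. The trial randomises and samples a blinded concurrent control that could remove any change common to both arms, but the named analysis replaces that control with an assumption.

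A significant pooled result would show that treated participants changed over time. Section 10.4.2 would have it read as an effect of treatment. Plots and separate within-arm p-values do not repair this, because a significant active arm beside a non-significant placebo arm is what unequal group sizes tend to produce even when both arms shift equally. The Summary in section 2.2 names a larger phase II study as a possible next step if the goals are met, so the attribution has consequences.

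**Working it through.** **Inputs.** From 10.4.2: paired t-test, two-sided 0.05, n=11 per dose and n=33 pooled, effects in SD units of change because no SD estimate is available. From 10.3 and 10.4: 12 active and 3 placebo per cohort, so 9 placebo. My assumptions: equal SD of change in both arms; 9 evaluable placebo, or 8 if one is lost.

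**1. The protocol's own power.** Noncentral t, n−1 df, noncentrality d√n.
- n=11, d=0.94: power 80.2%; Φ(0.94)=0.83.
- n=33, d=0.504: power 80.2%; Φ(0.504)=0.69.

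All four stated figures reproduce. The arithmetic is right; the question is what the test can support.

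**2. Can placebo alone verify zero change?** The 95% CI half-width of a mean change is t(0.975, n−1)/√n.
- n=33: 2.037/√33 = 0.35 SD.
- n=9: 2.306/√9 = 0.77 SD.
- n=8: 2.365/√8 = 0.84 SD.

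Even an observed placebo change of exactly zero would leave untreated shifts beyond 0.504 SD inside the interval. A paired test in 9 placebo recipients reaches 80% power only at 1.07 SD.

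**3. If the assumption fails.** The protocol gives no drift estimate, so these values are illustrations. There is no drug effect, and the same mean drift applies in both arms. The last column takes the arms as independent: P(n=33 rejects) × [1 − P(n=9 rejects)]; at 0.2 SD, 0.200 × (1 − 0.083) = 0.183.

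| Assumed drift (SD) | Pooled active, n=33, rejects | One dose group, n=11, rejects | Placebo, n=9, rejects | Active significant, placebo not |
|---|---|---|---|---|
| 0.1 | 8.6% | 6.0% | 5.8% | 8% |
| 0.2 | 20% | 9.2% | 8.3% | 18% |
| 0.3 | 39% | 15% | 13% | 34% |

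A simulated two-sample test on change scores (33 v 9) stays at 5.0% at each of these drifts, because the common shift cancels.

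**4. What the between-arm contrast can deliver.** Unadjusted half-width: t(0.975, n₁+n₂−2) × √(1/n₁+1/n₂).
- 33 v 9: 2.021 × √(1/33+1/9) = 2.021 × 0.376 = 0.76 SD; 80% power at 1.08 SD; 26% power at 0.504 SD.
- 33 v 8: 2.023 × 0.394 = 0.80 SD; 80% power at 1.13 SD; 24% power at 0.504 SD.

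**The case against.** The strongest reply has five parts.

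- **It belongs in the SAP.** Section 10.2 sends secondary outcomes to a SAP that is not at hand, and an unpowered supportive contrast could sit there. But the protocol has not left the method open: it names the test, the population and the interpretation. Those are the points at issue.
- **The test fits its objective.** Objective 1.3.1 asks only about change after cemiplimab, and 1.3.2 belongs to a different outcome measure. This stands: the paired test is a proper answer to 1.3.1. It does not license the causal label in 10.4.2 or meet the purpose for placebo given in 10.4.
- **Other evidence bears on attribution.** Section 10.6.2 plans dose-response regressions and 11.2.2 plans PK/PD modelling; a common drift would not by itself produce a gradient. This stands in part. Such analyses could support a drug effect, but the cohorts enrol sequentially, so dose is not randomised, and no placebo contrast is stated in them.
- **Drift is unlikely.** Entry requires at least 24 months of ART and a stable regimen, and excludes recent vaccination and immunomodulators. Eligibility does not select on CD8+ response, and values are averaged over several visits. All fair, and the assumption is disclosed. These points make zero change plausible; they do not test it.
- **Nine placebo recipients are too few for any contrast.** The rationale for placebo in section 2.2 is about adverse events, and the contrast is no more precise than the placebo mean alone. True. Its advantage is that a common change cancels out, and its width shows honestly what the trial can say about a drug effect.

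**Conclusion.** The concern holds. The CD8+ plan supports a statement about within-arm change, while 10.4.2 labels it a treatment effect and 10.4 promises a comparison that 10.6.2 does not contain. On the protocol's own sample sizes, placebo seen in isolation cannot exclude an untreated change as large as the pooled target (half-width 0.77 v 0.504 SD). This rests on equal SDs of change and nine evaluable placebo recipients; with eight it is slightly worse. The inflated rejection rates are conditional on drift values the protocol does not supply, and they show sensitivity, not likelihood.

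The change should be made, but it is of modest weight in a phase I/II study whose primary objective is safety. The power figures are correct. The plots, the disclosure of the assumption and the models for the single-copy assay are not criticised.

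**What to change.** In 10.6.2, add a baseline-adjusted difference, cemiplimab minus pooled placebo, in the week 2–12 average CD8+ response with a 95% CI, and the same for the measures that follow the paired-t approach. Use the as-treated set already defined and present the result as an estimate, not a powered test. Keep the paired t-tests as within-arm summaries, and state that a drug effect will not be inferred from them alone or from comparing separate arm p-values. In 10.4.2, replace the treatment-effect wording with mean within-arm change. Say also that the contrast removes a change common to both arms but, on the as-treated set, is not a full intention-to-treat comparison.

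The cost is one small analysis on data already being collected, with no extra participants or samples. The drawback is precision: by itself the contrast can neither confirm nor exclude the 0.504 SD target. Baseline adjustment should narrow the interval, by an amount the protocol gives no basis to state.
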